10. ETHICAL CONSIDERATIONS

10.1 Regulation statement

The study will be conducted according to the principles of the Declaration of Helsinki (2008) and in accordance with the Medical Research Involving Human Subjects Act (WMO).

10.2 Recruitment and consent

Patient recruitment and informed consent will be obtained by [name] and [name] from the Department of Internal Medicine, Division of Haematology. When informed consent is signed the Department of Nuclear Medicine and Molecular Imaging will schedule the FDG-PET-CT within 48 hours from the HR-CT and inform the patient about the scan procedure. Patients may withdraw from this study at any time, without prejudice to further treatment. The patient information letter and informed consent form are attached as separate documents.

10.3 Objection by minors or incapacitated subjects (if applicable)

This is not applicable in this study.

10.4 Benefits and risks assessment, group relatedness

The patients who are participating in this study will not have benefits from this scan in the way that their treatment decisions will not depend on the results of FDG-PET-CT scans. Diagnostic and treatment procedures will be followed as normal. We hope this pilot study will reveal that FDG-PET-CT is a valuable tool for the diagnosis and evaluation of treatment in this patient group and that in the future this imaging tool can be used as the imaging method of choice.

10.5 Compensation for injury

The sponsor/investigator has a liability insurance which is in accordance with article 7, subsection 6 of the WMO.

The sponsor (also) has an insurance which is in accordance with the legal requirements in the Netherlands (Article 7 WMO and the Measure regarding Compulsory Insurance for Clinical Research in Humans of 23th June 2003). This insurance provides cover for damage to research subjects through injury or death caused by the study.

1. € 450.000,-- (i.e. four hundred and fifty thousand Euro) for death or injury for each subject who participates in the Research;

2. € 3.500.000,-- (i.e. three million five hundred thousand Euro) for death or injury for all subjects who participate in the Research;
3. € 5.000.000,-- (i.e. five million Euro) for the total damage incurred by the organisation for all damage disclosed by scientific research for the Sponsor as 'verrichter' in the meaning of said Act in each year of insurance coverage.

The insurance applies to the damage that becomes apparent during the study or within 4 years after the end of the study.

10.6 Incentives (if applicable)

This is not applicable in this study.

11. ADMINISTRATIVE ASPECTS AND PUBLICATION

11.1 Handling and storage of data and documents

Medical history and data from this study will be used for scientific purposes. Medical history data include: history of disease, diagnostic and therapeutic data, other scans performed, results of HR-CT, BAL and galactomannan tests and laboratory parameters. Study data include: data of the FDG-PET-CT scan. Data of the patients will be coded in our research database. Only the project leader and the principal investigators of the study will have access to the patient data. Names of patients will not be visible in scientific publications. Data will be stored after finishing the data analysis. Digital data are protected by our local hospital information system. This will also protect the data to dissemination outside the hospital. No reports of the patients of our protocol will appear in the hospital system.

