Treatment of IFIs remains, even when recognized early, problematic because the response of a patient on antifungal treatment depends on the depth and the duration of this immunosuppressed (mostly granulocytopenic) condition. Therefore, it is essential to diagnose IFIs and start the right treatment as soon as possible to increase survival rates of the patients. It is therefore of invaluable importance to have an imaging method for diagnosing these IFIs that has a higher sensitivity and specificity than the HR-CT with and without the galactomannan-test. Therefore, we want to study the added value of FDG-PET-CT compared to the HR-CT with and without a positive galactomannan-test.

¹⁸F-FDG-PET, and even better the combined PET-CT scan (which correlates anatomic with pathophysiologic imaging), will maybe be this important non-invasive imaging technique to early diagnose IFIs.

FDG-PET is used already for many years in daily practice in many infectious diseases. This technique is also used incidentally in various fungal infections, such as aspergillosis, candidiasis, histoplasmosis, coccidioidomycosis, cryptococcosis and *Pneumocystis jiroveci*. [3-9] However, systematical use of FDG-PET in patients suspected of IFIs is virtually absent.

Sometimes these infections were found by coincidence in patients that were scanned for other reasons such as (recurrent) malignancy.

The largest study was published by Chamilos et al. who reported their own experiences in 13 patients with the results of nine patients in literature. Most patients had an underlying malignancy (73%), primarily of haematological origin (55%) and 7 were allogeneic haematopoietic stem cell transplants recipients. Importantly to notice, the vast majority of these immunocompromised patients (82%) were non-neutropenic at the time of diagnosis of IFI. They found that FDG-PET frequently found occult lesions not found with other imaging techniques (3 out of 16 patients with available follow FDG-PET imaging studies), and that the results helped to determine treatment length in 8 of these 16 patients. Overall, FDG-PET was deemed to be helpful in 10 out of the 16 (60%) eligible patients. [10] However, it remains unclear whether these results also apply for neutropenic patients.

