2. OBJECTIVES

Primary Objective:

To evaluate if FDG-PET-CT has added value compared to HR-CT and galactomannan-test, nowadays the silver (or surrogate gold) standard diagnostic techniques for early diagnosing IFIs in neutropenic patients. To evaluate this added value we have the following questions:

- Has FDG-PET-CT additional value as imaging modality compared to the HR-CT thorax? Are their specific imaging characteristics found on FDG-PET-CT in relation to the 3 different described lesions found by HR-CT? Can FDG-PET-CT also provide information about the extension of the known lesions, i.e. is the halo sign on HR-CT involved in the infectious process or is it a sign of decreased perfusion due to infarction?
- Can FDG-PET-CT detect enlarged and/or positive lymph nodes and what is the meaning of these lymph nodes in relation to prognosis or GM detection?
- Is FDG-PET-CT able to find additional infectious lesions that are not visible on HR-CT of the thorax? Can FDG-PET-CT detect smaller lesions than HR-CT by its metabolic positivity and is there a relation between the total amount of metabolic positivity of lesions (mean SUV times area of positivity) and galactomannan positivity, which is a parameter of activity and/or invasiveness of aspergillosis?
- Is FDG-PET-CT able to find additional infectious lesions that are not visible on HR-CT of the thorax because they are found outside the thorax? Sometimes IFI are found in the sinussen or gut or brain or combinations of these localisations.

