7.3 Study procedures

When the (conventional) diagnostic tools are performed and a patient probably or possibly has an invasive fungal infection, FDG-PET-CT (low dose CT) scan will be planned as soon as possible, but within 48 hours of the HR-CT scan on the mCT camera (Siemens).

When the (conventional) diagnostic tools are suspicious for an IFI antifungal treatment will be started, independent of the FDG-PET-CT results. Treatment will be continued conform normal treatment procedures, i.e. treatment regime will not depend on the results of the FDG-PET-CT.

Patient recruitment:

Informed consent will be obtained by [name] or [name] from the Department of Internal Medicine, Division of Hematology. When the patient decides to participate he/she will be asked to sign the informed consent form. The normal diagnostic and therapy protocols will not be changed; other imaging studies will not be delayed. Patients can contact an independent doctor (Dr. [name]) in case they feel the need to receive information from a doctor who is not involved in the study.

Preparation and labelling of [¹⁸F]-FDG:

¹⁸F-FDG will be prepared according to the standard protocol at the department of Nuclear Medicine and Molecular Imaging as is described in the IMPD.

[¹⁸F]-FDG-PET-CT protocol:

A routine whole body PET (that means from head till halfway the upper legs) will be performed 60 minutes after the intravenous injection of 3-5 MBq per kilogram [¹⁸F]-FDG conform normal administrated activity in patients. A low dose CT will be

performed simultaneously for attenuation correction and for anatomic correlation with the PET images. The total scanning time will be around 25 minutes.

Evaluation of the FDG-PET-CT scan:

The FDG-PET-CT will be evaluated qualitatively and quantitatively by an experienced nuclear medicine physician, with special attention to finding lesions outside the thorax, the extension of the lesions found compared to the HR-CT lesions and to the intensity of the uptake of FDG by calculating the SUVmax. These quantitative results will be compared to the results of the galactomannan-tests.

Radiation dose considerations:

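### Lesions outside the thorax are a stated search target, but section 11.1 keeps all reports out of the hospital system and the protocol gives no route for telling the treating team

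*Protocol*

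**What the plan says.** Section 2 (Objectives) lists among the questions under the primary objective: "Is FDG-PET-CT able to find additional infectious lesions that are not visible on HR-CT of the thorax because they are found outside the thorax". It names the sites: "Sometimes IFI are found in the sinussen or gut or brain or combinations of these localisations".

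Section 7.3 (Study procedures) sets a field of view that covers those sites, "A routine whole body PET (that means from head till halfway the upper legs) will be performed", and has the scan read "with special attention to finding lesions outside the thorax". On care, the same section says: "Treatment will be continued conform normal treatment procedures, i.e. treatment regime will not depend on the results of the FDG-PET-CT". Section 10.4 repeats that treatment decisions are independent of the scan.

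Section 11.1 (Handling and storage of data and documents) states: "Only the project leader and the principal investigators of the study will have access to the patient data". It ends: "No reports of the patients of our protocol will appear in the hospital system". Neither sentence carries an exception.

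**The concern.** Section 1 points out that HR-CT of the thorax does not show lesions outside the lungs. The study scan may therefore show a brain, gut or sinus lesion that usual care has not detected. Such a lesion is one of the results the study is looking for, so this goes beyond ordinary incidental findings.

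The protocol also describes invasive fungal infection as life-threatening and says that early diagnosis is essential. Yet its reporting rule keeps the scan report out of the hospital system in every case, and its access rule does not name the treating team. A site following 11.1 literally could hold a clinically important finding in the research data while the patient's record shows nothing.

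**Working it through.** The point concerns procedure, and the plan has no figure to reproduce. The check is whether any section carries a PET finding to the treating physician.

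**Sections side by side**

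| Section | What it provides | Route to the treating team? |
|---|---|---|
| 2, 7.3 | Search for extrathoracic lesions; head-to-thigh scan | None stated |
| 7.3, 10.4 | Treatment independent of PET | Governs decisions; silent on communication |
| 8.1 | Section 10 WMO event: disadvantages of participation greater than foreseen | Does not concern scan findings |
| 8.2 | Adverse events reported by the subject or observed by the investigator or staff; SAEs go to the METC | A lesion already present and seen on a scan is not clearly an adverse event; the SAE route leads to the ethics committee |
| 8.3 | Follow-up of adverse events, possibly with referral to a physician | Applies only once something is classed as an adverse event |
| 10.2 | Consent taken by Division of Haematology staff; information letter attached separately | Letter not shown |
| 11.1 | No reports in the hospital system; access for project leader and principal investigators | None; the usual channel is closed without exception |

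No section supplies the route. In 11.1 the gap comes from a stated rule and not only from silence.

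**How often might it arise?** The only relevant figure is in section 1, on the largest published series: "They found that FDG-PET frequently found occult lesions not found with other imaging techniques (3 out of 16 patients".

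- Proportion: 3/16 = 0.1875.
- Expected number in 12 patients: 12 × 0.1875 = 2.25.
- Chance of at least one in 12: 1 − (13/16)^12 = 0.917, or 92%.
- Exact 95% interval for 3/16: 0.040 to 0.456. This gives 0.49 to 5.48 patients and a chance of at least one between 39% and more than 99%.

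The arithmetic is sound, but the input measures something else:

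- The 3 patients had occult lesions at any site. They are not described as extrathoracic, urgent or unknown to the treating team.
- The denominator is patients with follow-up PET, taken from a pooled series (13 own cases plus nine from the literature, 22 in all). It is not patients scanned once at diagnosis.
- Section 1 says that 82% of the series were non-neutropenic and that it is unclear whether the results carry over to neutropenic patients.

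The binomial interval covers sampling error only and reflects none of these differences.

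**The case against.** The strongest reply is that 11.1 is a confidentiality clause and prohibits no conversation. It limits access to research data and keeps reports out of the hospital system, but it does not bar an investigator from speaking to the treating physician. Patients come from the Division of Haematology and its staff take consent, so investigators and treating staff may well overlap; with names removed, this cannot be excluded. The information letter may deal with unexpected findings. Searching for lesions while not basing treatment on an unvalidated scan is also a coherent pilot design, and section 10.4 is open about the lack of benefit.

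Much of this stands. A reader might infer that the protocol blocks communication or that the team will not be told; the text supports only that no route is described. A reader might also infer that the scan is expected to reveal unknown disease. Section 9 says the opposite: additional lesions elsewhere in the body cannot be predicted. Section 8 cannot be dismissed outright either, since whether a lesion seen by staff counts as an adverse event is arguable.

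What does not stand is the conclusion that nothing needs changing. Informal overlap is not a procedure. If the letter does promise that findings will be passed on, the unqualified sentence in 11.1 should still be reconciled with it. Independence of treatment from PET is a separate matter from telling the treating physician what was seen.

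**Conclusion.** The concern holds in a limited form. The protocol searches for extrathoracic lesions, closes the normal reporting channel without exception, and describes no other. Followed as written, an unexpected, clinically important finding would be absent from the patient's record, and its communication would be left to chance. This rests on the protocol alone; the information letter could narrow the gap but has not been seen.

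No reliable size can be given. About 2 of 12 patients is illustrative at most. A reader might take the 92% as the chance of an uncommunicated serious finding, but for the reasons shown in the working it is not.

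A reader might also infer that reporting findings would leave the study wholly unaffected. That is too strong. Sections 7.1.1 to 7.1.3 define no later endpoint, and HR-CT and galactomannan testing come before the scan, so the imaging comparison is protected once the reading is locked. But section 2 asks what lymph nodes seen on PET mean for prognosis, and a change in care after notification could affect that question. Section 7.3 also does not say that antifungal treatment has begun by the time of the scan, only that it starts regardless of the PET result.

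**What to change.** Reconcile sections 2, 7.3, 10.4 and 11.1:

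- Qualify the closing sentence of 11.1 to state who is told of an unexpected, clinically important finding, how and when.
- Place this step after the study reading has been completed and locked.
- Log each notified case with its date, and list the cases in the study report.
- Make 7.3 and 10.4 consistent with this communication route, and check that the patient information letter agrees. The principle that treatment is independent of PET need not be rewritten. Any clinical action is for the treating physician and outside this review.

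The cost is a short wording amendment and one log. Because it bears on subjects' safety, it would probably count as substantial under section 11.2 and need notification. The downsides are some false-positive notifications and, in notified patients, care that may no longer be fully independent of PET. The log would show which patients those are when the prognosis question is described.

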11.2 Amendments

A 'substantial amendment' is defined as an amendment to the terms of the METC application, or to the protocol or any other supporting documentation, that is likely to affect to a significant degree:

- the safety, or physical or mental integrity of the subjects of the trial;
- the scientific value of the trial;
- the conduct or management of the trial; or
- the quality or safety of any intervention used in the trial.

All substantial amendments will be notified to the METC and to the competent authority.

Non-substantial amendments will not be notified to the accredited METC and the competent authority, but will be recorded and filed by the sponsor.

11.3 Annual progress report

The sponsor/investigator will submit a summary of the progress of the trial to the accredited METC once a year. Information will be provided on the date of inclusion of the first subject, numbers of subjects included, and numbers of subjects that have completed the trial, serious adverse events/ serious adverse reactions, other problems, and amendments.

11.4 End of study report

The sponsor will notify the accredited METC and the competent authority of the end of the study within a period of 90 days. The end of the study is defined as the last patient's last visit.

In case the study is ended prematurely, the sponsor will notify the accredited METC and the competent authority within 15 days, including the reasons for the premature termination.

Within one year after the end of the study, the investigator/sponsor will submit a final study report with the results of the study, including any publications/abstracts of the study, to the accredited METC and the Competent Authority.

11.5 Public disclosure and publication policy

The results of this study will be published in medical scientific journal(s) by the coordinating investigator ([name]) and the principal investigators. There is no arrangement made concerning the public disclosure and publication of the research data.

